### **9.9.2 Responsibilities of the coordinating investigator (CI) and in Germany "Leiter klinische Prüfung" (LKP)**

Responsibilities of the coordinating investigator are among others:

- Give input and advice for the protocol creation and possible amendments, medical review
- Consulting and support in case of clinical or organizational issues arising during the conduction of the study
- Advising all investigators in medical questions connected to the study
- Support of reporting to CA, if applicable
- Signature of Clinical Investigation Plan (CIP) and Clinical Investigation Report (CIR)

## 10 MONITORING PLAN

The responsibility of BIOTRONIK SE & Co.KG as sponsor and BIOTRONIK Inc. as local sponsor in the U.S. is to ensure protocol and regulatory compliance through proper monitoring of the study.

BIOTRONIK is required to ensure that the BioMonitor is used under the immediate direction of an investigator. As the investigator, the physician is responsible for conducting the study in accordance with the signed clinical investigation agreement, the study protocol, applicable laws, and FDA and/or local regulations (e.g. 21 CFR, parts 50, 54, 56, and 812, ISO 14155, Declaration of Helsinki) and any conditions of approval imposed by the reviewing IRB/EC.

A monitor (authorized BIOTRONIK personnel, Clinical Research Associates (CRAs)/Monitor, or by authorized BIOTRONIK designees) will visit the study site periodically during the study. All participating sites will be monitored during the course of the study with visits occurring as frequently as deemed necessary to ascertain adherence to the protocol procedures, as well as maintenance of the highest data quality. A detailed monitoring plan developed by BIOTRONIK will be followed.

The entries in the electronic eCRF will be reviewed and source data verified at the investigational site by monitors as specified in the monitoring plan to ensure that the investigator and the clinical investigation team conducts the clinical investigation in accordance with the CIP, Declaration of Helsinki, ISO 14155 or ICH-GCP (U.S. sites), and applicable FDA and local laws and regulations to ensure adequate protection of the rights, safety and wellbeing of subjects and the quality and integrity of the resulting data.

Periodic monitoring visits will assure, amongst others, that the facilities are still performing well; that the CIP is being followed, that the EC/IRB/CA has been informed about approved CIP changes as required, that records on study conduct and data collection are complete and present, that appropriate and timely reports have been made to the sponsor and the authorities, and that the investigator is carrying out all agreed activities.

During the periodic monitoring visits, assessments of the study site will include but will not be limited to the following:

1. Completion and submission of the required eCRFs including source data verification (SDV) and data plausibility checks
2. Completion and submission of other applicable study documentation
3. Continued acceptability of the facilities, including storage and maintenance of investigational inventory
4. Adherence to reporting timelines for adverse events
5. Adherence to the CIP
6. Adherence to ISO 14155 or ICH-GCP (for U.S. sites) and applicable FDA and local regulations and laws

If a monitor becomes aware that an investigator is not complying with the requirements mentioned above, the monitor is obliged to notify BIOTRONIK study management.

BIOTRONIK will evaluate the non-compliance and issue corrective actions, discontinue enrollment or as a last measure close the clinical investigation site (see section 14.4)

The investigators are obliged to provide adequate access to the original patient records and other relevant source data related to the clinical study. Adequate manned and spatial resources have to be provided for all monitoring activities. The investigational sites are asked to collaborate closely with the clinical monitor. The investigational sites are obliged to keep the source data (e.g. patient records) and CRF-entries up-to-date to ensure efficient and time-saving monitoring.

Agreement to monitoring activities was obtained from the patient in the ICF. Detailed monitoring activities and monitor responsibilities are listed in the monitoring plan.

## 11 STATISTICAL CONSIDERATIONS

### 11.1 Statistical design, method and analytical procedures

The study was statistically designed to allow for early discontinuation in case of superiority and to adapt the sample size in case of positive results but insufficient power to meet the statistical significance with the initially planned sample size.

#### 11.1.1 Statistical design

According to the original statistical planning, the study was designed as a three-stage adaptive group sequential test procedure according to O'Brien Fleming with survival endpoint, where the inverse normal method is used to combine the separate stage information. This strategy is replaced with a single final analysis of all data after study termination.

The first interim analysis has been performed. The planned second interim analysis will not be done. Due to the O'Brien Fleming design with a very low  $\alpha_1 = 0.00025$  for the first interim analysis, an adjusted significance level for the final analysis  $\alpha_{\text{final}} = 0.02476$  will maintain the global 1-sided significance level  $\alpha = 0.025$ .

#### 11.1.2 Full Analysis set based on the ITT principle

The analysis of the primary hypothesis is performed on the full analysis set based on the intention-to treat (ITT) principle; i.e. the set of data from all randomized patients by minimal and justified elimination of subjects. This set is used to estimate the effect of the experimental intervention with greatest external validity. Subjects allocated to a randomization group are analysed as members of that group irrespective of their compliance to the planned course of treatment, e.g. cross-over to the other group.

The ICH-E9 guideline states that "there are a limited number of circumstances that might lead to excluding randomized subjects from the full analysis set including ... the failure to take at least one dose of trial medication and the lack of any data post randomization."

In accordance to this guideline, the following patients will be excluded from the analysis set

- Patients of the BioMonitor group and control group in case of a drop-out before discharge from the index hospitalization
- Patients without signed informed consent form

#### 11.1.3 Per-Protocol Analysis Set

A supportive analysis of the primary hypothesis is performed on the per-protocol set (efficacy sample), which is a subset of the patients from the above full analysis set who complied sufficiently with the protocol. This set is used to ensure that the data would be likely to exhibit the effects of treatment according to the underlying scientific model.

The Per-Protocol Analysis Set is the subgroup of the Full Analysis set after exclusion of

- Patients with violation of in- or exclusion criteria at enrollment
- Patients with major deviations from the CIP in accordance with the definition given in section 14.1
- Patients of the BioMonitor group without implanted device or drop-out less than 1 month after implantation
- Patients of the control group in case of a drop-out less than 1 month after index hospitalization

Time-to-first-event data are censored after occurrence of

- Cross-overs from the BioMonitor group to the control group or vice versa
- Major protocol violations as defined in section 14.1

Primary endpoints are not taken into account in the BioMonitor group and in the control group until 1 month after discharge from the index hospitalization.

#### **11.1.4 Statistical methods**

Descriptive analyses: The data are presented using descriptive statistical methods. For metric data sets, the mean values, standard deviation, median, maximum and minimum are stated, if appropriate. Ordinal data are described by the median and interquartile range. For nominal data, absolute numbers and relative frequencies are determined.

Inferential analysis of the primary hypothesis: A one-sided log rank test is performed in the context of a confirmatory analysis of the primary hypothesis at the interim and the final analysis.

Explorative multivariable analyses are performed (after the termination of the study, i.e. not after interim analysis) based on the Cox regression model.

Inferential analysis: For the inferential analysis of metric, normal-distributed data, a t-test for interindividual of independent groups or a paired t-test for the intraindividual comparison of paired data is performed. In case the normality assumption of the data is either a priori not justified as specified in the SAP or overtly violated (i.e. by a significant Kolmogorov-Smirnov-Lilliefors or Shapiro-Wilk test result) a non-parametric Wilcoxon-Mann-Whitney rank-sum test or a Wilcoxon-signed-rank test is performed, respectively. For the analysis of relative frequencies, Fisher's exact test is used.

## **11.2 Sample size**

The original planning assumed that 372 primary events would be required to accept the primary alternative hypothesis with 80% statistical power given an assumed hazard ratio in the population of 0.7452, and the study was to be terminated after this number of endpoints had been collected.

Instead, it was decided to enter the termination phase without any avoidable further delay. Therefore, the intended number of endpoints may not be reached.

### 11.3 Level of significance and the power of the study

The global significance level of the 1-sided hypothesis is 2.5%.

A statistical power of the final analysis of 80% was used for sample size calculation.

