### 8.9.1 Description of patient collective

Patients meeting the inclusion criteria and none of the exclusion criteria will be enrolled in the study. According to the sample size calculation (see section 11.2), up to 2900 patients will be enrolled into the study including 5 % drop-outs per year. The patient number is based on an expected endpoint-rate (see section 11.2) required to reach the study goal of 372 patients with one or more endpoint events. However, patient number will automatically be adapted in case the actual endpoint rate deviates from the expected rate. Thereby the limited number of patients to be excluded from the analysis set (see section 11.1.2) is not considered.

The enrolled subjects will be randomized in a 1:1 relation to the following study groups:

- BioMonitor group (best medical care and implanted with BioMonitor)
- Control group (best medical care)

By defining a termination visit (see section 8.2.4), the study protocol deviates from the initial planning with a defined number of primary endpoints.

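### The 372-event stop is dropped, but no power is given for the analysis that will be run, and a null primary result has no planned hazard ratio or confidence interval

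*Protocol*

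**What the plan says.** Protocol 11.2 assigns the sample size to the original planning: "372 primary events would be required to accept the primary alternative hypothesis with 80% statistical power". The planned effect behind this is a hazard ratio of 0.7452. The section then says that the study goes into termination without avoidable delay, and concludes: "Therefore, the intended number of endpoints may not be reached". Protocol 11.1.1 says of the group sequential design: "This strategy is replaced with a single final analysis of all data after study termination". It sets the final one-sided level at 0.02476. Protocol 11.3, the section named for the power of the study, adds only: "A statistical power of the final analysis of 80% was used for sample size calculation". Appendix A repeats the 11.2 text, SAP 5.9 repeats 11.2, and SAP 5.3 repeats 11.3.

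Other current text still assumes an event target:

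- Protocol 8.9.1 bases the patient number on the endpoint rate "required to reach the study goal of 372 patients with one or more endpoint events", and says the number adapts automatically if the rate differs from expectation. Its last sentence says that the termination visit departs from a planned number of primary endpoints.
- Protocol 8.1, copied in SAP 4, calls the design event-driven and makes the length of phase two depend on reaching the endpoints needed. Appendix A also calls the design event-driven.

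Protocol 11.5 defines success as acceptance of the primary alternative hypothesis. SAP 11.6 makes the primary Cox hazard ratios and 95% CIs conditional on that acceptance.

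**The concern.** A power figure for an event-driven log-rank test means something only at a stated event count. The plan has given up control of that count and put nothing in its place. A reader who looks up the power of the final analysis finds 80% and no other number, and can still find 372 described as the goal.

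This matters most for a non-significant result. With well under 372 events, the trial could have a large chance of missing the effect it was built to detect. The natural safeguard is the estimated hazard ratio with its CI, which shows what effects the data leave open. SAP 11.6 plans that estimate only after a positive test. SAP 11.5 offers Kaplan-Meier curves and survival times, and Protocol 11.1.4 mentions exploratory multivariable Cox models, but neither is a planned estimate of the primary treatment effect. SAP chapters 12 to 21 and 23 calculate hazard ratios for the secondary time-to-event endpoints without any such condition, so the primary endpoint would be the least informatively reported.

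**Working it through.** **Inputs.** Hazard ratio 0.7452, 372 events and 80% power (Protocol 11.2); one-sided global level 0.025 (Protocol 11.3); one-sided final level 0.02476 (Protocol 11.1.1); 1:1 allocation (Protocol 8.1); one-sided log-rank test (Protocol 11.1.4).

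**The plan's own figure.** −ln(0.7452) = 0.2941; z(0.025) = 1.960; z for 80% power = 0.8416.

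- Schoenfeld: 4 × (1.960 + 0.8416)² / 0.2941² = 363 events.
- Freedman: ((1 + 0.7452)/(1 − 0.7452))² × (1.960 + 0.8416)² = 369 events after rounding up.
- With the inflation factor of 1.0174 for three equally spaced O'Brien-Fleming stages: 369 and 375.

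All lie within 3% of 372, so the planning figure reproduces.

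**Power of the single final test at D events.** Power = Φ(0.2941 × √D / 2 − 1.9641), where 1.9641 = z(0.02476). The hazard ratio detectable with 80% power is exp(−2 × (1.9641 + 0.8416) / √D).

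| Events D | 0.2941 × √D / 2 | Power at HR 0.7452 | HR detectable with 80% power |
|---|---|---|---|
| 150 | 1.801 | 43.5% | 0.632 |
| 200 | 2.080 | 54.6% | 0.672 |
| 248 | 2.316 | 63.7% | 0.700 |
| 250 | 2.325 | 64.1% | 0.701 |
| 300 | 2.547 | 72.0% | 0.723 |
| 372 | 2.836 | 80.8% | 0.748 |

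Freedman's formula gives values about half a percentage point lower.

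**Where D might fall (assumption only).** No final or current count is given. SAP 5.7 reports 20 adjudicated endpoints in a June 2018 notice. SAP 5.8 plans the first interim at 124 endpoints, and SAP 5.5 cuts its data at 14 January 2020. The Protocol synopsis targets last patient out around October 2021. If the interim had exactly 124 events and the 20 belong to June 2018, the pace is 104 / 19 = 5.5 per month.

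- Constant pace: 124 + 5.47 × 21 = about 239 events, power 62%.
- Half that pace: about 181 events, 51%.
- 1.5 times that pace: about 296 events, 71%.
- Reaching 372 would need (372 − 124) / 21 = 11.8 per month, about 2.2 times the pace.

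**The case against.** The strongest reply is that nothing in Protocol 11.3 is false. It states in the past tense what was used for planning, and that is true. Section 11.2, directly above it, assigns 372 events and 80% to the original plan and discloses the possible shortfall. Section 8.9.1 itself notes the departure from a fixed endpoint number. All of this stands. A reader might infer that the plan claims 80% power for the curtailed analysis, or contains an arithmetic error. It does neither.

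The projection is also weak. The 124 is a planned trigger, not a reported count. The 20 equals the phase-one threshold, and its date is that of a newsletter. The pace was evidently rising: 20 events between August 2015 and June 2018, then 104 in 19 months on the same assumptions. Suppose the pace rose linearly from 1 per month in June 2018. An average of 5.47 then implies about 9.9 per month by January 2020, and holding that flat for 21 months gives about 333 events and 76% power. In addition, the reporting inconsistencies described in SAP 1.4 and the record review at the termination visit (Protocol 8.2.4) could change the count. So a reader might infer that the trial certainly ends below 372, or that 55–72% is its likely power, but the documents support neither statement.

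It can also be said that once the data are locked, a CI conveys precision better than planning power. That is right, and it is why the condition in SAP 11.6 matters: the better tool is withheld in the case where it is most needed.

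**Conclusion.** The point holds as an omission, together with leftover text that conflicts with the amended design. The only power in either document is a planning figure tied to an event count that the plan no longer requires. At hazard ratio 0.7452 and one-sided 0.02476, power falls from 80.8% at 372 events to 72.0% at 300 and 54.6% at 200. The chance of missing the design effect rises accordingly from 19% to 28% and 45%. These figures assume proportional hazards, 1:1 allocation and the Schoenfeld approximation. The actual event count is unknown, and any single projected value is an assumption.

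This point leaves the validity of the primary test untouched. What is unprotected is the reading of a non-significant result, because SAP 11.6 then plans no primary hazard ratio or CI.

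**What to change.** 1. In Protocol 11.2 and 11.3 and SAP 5.3 and 5.9, label 80% as the original planning figure at 372 events. Add a short table of power and detectable hazard ratio by event count, such as the one above, and report the pooled event count at database lock.
2. Reconcile Protocol 8.1 and 8.9.1, the excerpt of 8.1 in SAP 4, and the design row of Appendix A with Protocol 11.2. Remove the 372-event goal, the automatic adaptation of patient number and the event-dependent duration.
3. Amend SAP 11.6 so that the primary hazard ratio and 95% CI are reported whatever the test result, and state that a non-significant result will be interpreted from them.

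The cost is wording, one minor change to the analysis plan, and a stated power that looks less favourable. No test, significance level or analysis set changes. It should be done before lock. SAP 1.4 records that everyone responsible for SAP 3.0 was unblinded, but a table tied to the planned hazard ratio and pooled counts, and an unconditional estimate, cannot be suspected of following the observed treatment difference.

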### 11.4 Expected drop-out rate

A drop-out of 5% of the patients per year is expected. Thereby the limited number of patients to be excluded from the analysis set (see section 11.1.2) is not considered.

### 11.5 Pass/fail criteria

The pass criteria are to accept the primary alternative hypothesis based on the full analysis set.

### 11.6 Provision for an interim analysis

After the first phase, a blinded analysis of the total endpoint rate is planned. Because the blinding is not broken, this is not considered as an interim analysis. One interim analysis has been done, but no further interim analysis will be conducted.

### 11.7 Termination criteria

There is a blinded evaluation of the MACE rates after the event-check, which is no interim analysis because no therapy effect is investigated.

If the total number of patients with at least one MACE in both groups is less than 20 patients per 600 patient-years at the end of the event-check phase, the study will be terminated.

Furthermore, the sponsor may decide to discontinue the study due to organizational reasons based on the observed event rates and the general feasibility of the study. Based on the recommendations of the DSMB after the first interim analysis, the study will be stopped for futility when there is a low chance for rejection of the Alternative hypothesis at the final analysis or the need for an increase of the sample size, which is refused by the sponsor.

Stopping for superiority is achieved in case the 1-sided p-value at the interim analyses is below the O'Brien Fleming significance value  $\alpha_{\text{interim1}} = 0.00025$ .

### 11.8 Procedures for reporting of deviations to the statistical plan

Deviation(s) from the statistical plan described here are reported via amendments to the CIP and / or via a separate SAP.

An SAP version 1.0 was written as a separate document before 1st patient-in including a more technical and detailed elaboration of the statistical considerations as described here.

The SAP is reviewed and possibly updated based on a blind review of the data before breaking the blind for the interim analysis or the final analysis.

## 11.9 Specification of subgroups

Subgroups are predefined for exploratory analyses with respect to

- the occurrence of the predefined arrhythmias, and to
- the primary endpoint and other predefined outcomes.

The following subgroups are predefined according to their presentation at enrollment:

- All individual components of the CHADS2-score except the age-variable
- Age < median vs. ≥ median
- "Early enrollment" within 40 days of most recent MI vs. "late enrollment" after more than 40 days
- Men vs. women
- CHA2DS2-VASc-score ≤ 4 in men / ≤ 5 in women vs. ≥ 5 in men / ≥ 6 in women
- LVEF < median vs. ≥ median
- BMI: < 30 vs. BMI ≥ 30
- History of AF yes vs. no
- NSTEMI vs. STEMI
- History or presence of kidney failure yes vs. no

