#### 6.1.3 Benefits for future patients

If the study will be successful, it may show that patients matching the inclusion criteria benefit from ICM monitoring by reducing the risk for MACE. It may thereby contribute to a better treatment of post-infarct patients. If the study will fail to confirm the primary hypothesis, it may still provide information on subgroups with a benefit that will allow for the planning of confirmatory studies.

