## 5.6. Subgroups

### CIP chapter 11.9 Specification of subgroups

*Subgroups are predefined for exploratory analyses with respect to*

- *the occurrence of the predefined arrhythmias, and to*
- *the primary endpoint and other predefined outcomes.*

All subgroup analyses which are not pre-specified in the chapters 8 or following will be performed as ad-hoc analyses if needed.

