### CIP chapter 11.9 Specification of subgroups

*The following subgroups are predefined according to their presentation at enrollment:*

- *All individual components of the CHADS2-score except the age-variable*
- *Age < median vs. ≥ median*
- *"Early enrollment" within 40 days of most recent MI vs. "late enrollment" after more than 40 days*
- *Men vs. women*
- *CHA2DS2-VASc-score ≤ 4 in men / ≤ 5 in women vs. ≥ 5 in men / ≥ 6 in women*
- *LVEF < median vs. ≥ median*
- *BMI: < 30 vs. BMI ≥ 30*
- *History of AF yes vs. no*
- *NSTEMI vs. STEMI*
- *History or presence of kidney failure yes vs. no*

The subgroup "history of AF" defined in the CIP will not be considered for subgroup analyses. This variable is missing in the Baseline CRF because patients with history of atrial fibrillation and a CHADS-VASc score as required by the CIP are indicated to receive oral anticoagulation, which is an exclusion criterion. Thus, patients with history of AF are eligible for the study only in exceptional cases and their number is insufficient for subgroup analyses.

Subgroups CHADS2

[figure not shown]
Subgroups with respect to all individual components of the CHADS2 score except the age variable, which is grouped according to the median.

Data file: Identifier patient_display_id_full	Notes	Variable name	Variable label	Variable level	Nominal values
data_SAR	descr.	subgroups_chads2_c_SAR 	Subgroups Congestive Heart Failure	nominal	0 / 1
data_SAR	descr.	subgroups_chads2_h_SAR 	Subgroups hypertension	nominal	0 / 1
data_SAR	descr.	subgroups_chads2_d_SAR 	Subgroups diabetes mellitus	nominal	0 / 1
data_SAR	descr.	subgroups_chads2_s_SAR 	Subgroups stroke or TIA or systematic thromboembolic event	nominal	0 / 1

Subgroups other

Median cut-offs are based on the ITT analysis set.

Data file: Identifier patient_display_id_full	Notes	Variable name	Variable label	Variable level	Nominal values
data_SAR	descr.	subgroups_age_ge_median_SAR 	Subgroups age < median (0) vs ≥ median (1)	nominal	0 / 1
data_SAR	descr.	subgroups_mi_enr_ge_41d_SAR 	Subgroups enrollment after most recent MI < 41days (0) vs ≥ 41 days (1)	nominal	0 / 1
data_SAR	descr.	subgroups_gender_SAR 	Subgroups gender men (0) vs women (1)	nominal	0 / 1
data_SAR	descr.	subgroups_cha2ds2vasc_SAR 	subgroups CHA2DS2-VASC low (0) vs high (1)	nominal	0 / 1

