## 11. Primary Endpoint

### 11.1. Analysis set

Any interim analysis is based on the ITT analysis set.

All analyses for the final statistical analysis report are based on the ITT analysis set and the per-protocol analysis set. Thereby, subgroup analyses are performed for the ITT analysis set only.

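### Age and LVEF are pre-specified as effect modifiers only as splits at the trial's own median, which loses about one third of the information if the treatment effect changes smoothly with them

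*Protocol*

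**What the plan says.** Protocol 11.9 lists the subgroups, among them "Age < median vs. ≥ median" and "LVEF < median vs. ≥ median". Their status is clear: "Subgroups are predefined for exploratory analyses with respect to" the predefined arrhythmias, the primary endpoint and other outcomes.

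SAP 5.6 codes each as a 0/1 variable and adds: "Median cut-offs are based on the ITT analysis set". For the primary endpoint, SAP 11.1 states: "Thereby, subgroup analyses are performed for the ITT analysis set only". SAP 9.2 lists age at enrollment and LVEF at scale level, so the continuous values are available.

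Two other provisions could touch the question. Protocol 11.1.4 says "Explorative multivariable analyses are performed" with a Cox model, without naming covariates, functional form or interactions. SAP 5.6 says: "All subgroup analyses which are not pre-specified in the chapters 8 or following will be performed as ad-hoc analyses if needed". No interaction test is named for any subgroup.

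Protocol 6.1.3 says that, should the primary hypothesis fail, "it may still provide information on subgroups with a benefit that will allow for the planning of confirmatory studies".

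**The concern.** A 0/1 split treats every patient below the median as alike and every patient above it as alike. If the effect of monitoring changes gradually with age or LVEF, much of that gradient lies within the two halves and is averaged away.

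The cut-off is also a product of who was enrolled. It is unknown until the data are in, will differ between trials and is tied to no clinical threshold. The same protocol uses fixed cut-offs elsewhere: 30 for BMI in 11.9, and 65 and 75 years in the CHA2DS2-VASc definition in 8.9.2.1.

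At stake is the hypothesis-generating use described in Protocol 6.1.3. Events are already scarce, because Protocol 11.2 says the intended number may not be reached. A coding that discards information makes a real gradient harder to see.

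**Working it through.** **Inputs from the documents.** Hazard ratio 0.7452, 372 events and 80% power (Protocol 11.2 and 11.3); one-sided 2.5% (11.3); 1:1 allocation (8.1); three-stage O'Brien-Fleming as the original design (11.1.1). The documents give no figure for the loss from a median split.

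**Assumptions.** Log-linear effect modification of 0.20 or 0.30 in log hazard ratio per SD; events divided equally between arms and between halves; a two-sided 5% interaction test; 250 events as an example of a shortfall.

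**1. The plan's own event number.**
- Schoenfeld: 4 × (1.960 + 0.842)² / (ln 0.7452)² = 363.
- Freedman: (1.960 + 0.842)² × (1.7452 / 0.2548)² = 368.2, so 369.
- Three equally spaced O'Brien-Fleming looks inflate this by 1.017, giving 370 (Schoenfeld) or 375 (Freedman).

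All are within 3% of 372, so 372 is a sound base for what follows.

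**2. Information kept by a median split.** Relative to a linear term, the efficiency is the squared correlation between X and the indicator that X is at or above its median. For a normal X this is 2/π = 0.637, a loss of 36%. In these terms 372 events act like 372 × 0.637 = 237. Other shapes, by simulation with 1,000,000 draws each:

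| Covariate shape (assumed) | Loss |
|---|---|
| Uniform | 25% |
| LVEF normal (mean 45–55, SD 8–10), truncated above 35 | 34–35% |
| Skew-normal | 38% |
| LVEF rounded to 5 points | 39% |
| t with 5 df, lognormal, exponential | 46–52% |

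**3. Effect on interaction power.** With D events, the log hazard ratio in each half has variance 4/(D/2). The difference between halves therefore has SE 4/√D. The continuous interaction per SD has SE 2/√D. For a normal covariate with slope β per SD, the two halves differ on average by 2√(2/π) × β = 1.596β.

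At D = 372 the SEs are 0.207 (split) and 0.104 (continuous). For β = 0.20:
- Split: z = 0.319 / 0.207 = 1.54, power 34%.
- Continuous: z = 0.20 / 0.104 = 1.93, power 49%.

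| Events | β per SD | Split: z, power | Continuous: z, power |
|---|---|---|---|
| 372 | 0.20 | 1.54, 34% | 1.93, 49% |
| 372 | 0.30 | 2.31, 64% | 2.89, 82% |
| 250 | 0.20 | 1.26, 24% | 1.58, 35% |
| 250 | 0.30 | 1.89, 47% | 2.37, 66% |

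**4. If the truth is a step.** For a normal covariate, the share of the true pattern captured (R²) is:

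| True step at percentile | Median split | Linear term |
|---|---|---|
| 50th | 1.00 | 0.64 |
| 60th | 0.67 | 0.62 |
| 70th | 0.43 | 0.58 |
| 90th | 0.11 | 0.34 |

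The split is better only when the step lies near the median.

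**The case against.** The strongest reply is that this is a modelling preference about exploratory analyses. The subgroups are labelled exploratory, and SAP 5.6 marks the variables for descriptive reporting. Since no interaction test is named, the power figures compare two tests that the plan does not contain. That stands. The figures show how much information each coding keeps; they do not show a planned test to be underpowered. Protocol 6.1.3 is also a statement of possible benefit and not an analysis objective.

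A pre-stated median rule also has merits: it gives groups of similar size and cannot be tuned to outcomes. Age enters the CHA2DS2-VASc subgroup as well, through fixed bands. These points stand, but none recovers the information lost within the halves.

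A reader might infer that the plan rules out any continuous analysis. It does not: the multivariable Cox and ad-hoc provisions leave room for one. They commit to none, however.

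A reader might also infer that a median cut-off is useless to a later trial. The documents do not support that, since the observed median can be reported and applied elsewhere. Percentiles chosen to display a continuous effect depend on the sample too.

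On data quality, SAP 9.2 builds LVEF from two differently timed measurements, and SAP 9.3 does not impute missing baseline data. A linear LVEF term inherits both limits; so does the median split.

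**Conclusion.** The point holds as a low-severity improvement. A split at the trial's own ITT median is the only pre-specified handling of age and LVEF as effect modifiers. Under a roughly linear interaction it loses about one third of the information. The size depends on the covariate's shape and on linearity, neither of which the documents establish, and the loss is nil for a step at the median. The interaction sizes and the 250-event case are assumptions.

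It would be wrong to read this as a flaw in the main result: the stratified log-rank test and the 372-event calculation do not depend on it.

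**What to change.** In SAP 5.6, for the primary endpoint in the ITT set:
- Add treatment-by-age and treatment-by-LVEF terms, each variable continuous, to the STEMI/NSTEMI-stratified Cox model.
- Check linearity with a spline or quadratic term.
- Report each interaction estimate with its 95% CI, and the hazard ratio with 95% CI at stated values across the observed range. State how many patients contribute.
- Keep the median-split rows for display.
- Date the addition and label it exploratory and post hoc, because SAP 1.4 records that the persons responsible for SAP 3.0 were unblinded.

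The cost is some SAP text and extra analysis, with no new data. Protocol 13 treats changes that affect data analysis as substantial, but Protocol 11.8 lets deviations from the statistical plan be reported through the SAP alone. That route was used when SAP 2.0 dropped the subgroup on history of AF. The remaining downside is an assumed functional form, which the linearity check addresses.
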